5.2.6.1 Definitions of Adverse Events

Adverse event

An adverse event (AE) is defined as any untoward medical occurrence in a patient or clinical investigation subject administered a medicinal product and which does not necessarily have to have a causal relationship with this treatment.

Proprietary confidential information © 2020 Boehringer Ingelheim International GmbH or one or more of its affiliated companies

An AE can therefore be any unfavorable and unintended sign (including an abnormal laboratory finding), symptom, or disease temporally associated with the use of a medicinal product, whether or not considered related to the medicinal product.

Serious adverse event

A serious adverse event (SAE) is defined as any AE which fulfils at least one of the following criteria:

- results in death,
- is life-threatening, which refers to an event in which the patient was at risk of death at the time of the event; it does not refer to an event that hypothetically might have caused death if more severe.
- requires inpatient hospitalization
- requires prolongation of existing hospitalization,
- results in persistent or significant disability or incapacity,
- is a congenital anomaly / birth defect,
- is deemed serious for any other reason if it is an important medical event which, when based on appropriate medical judgement, may jeopardize the patient and may require medical or surgical intervention to prevent one of the other outcomes listed in the above definitions.

Examples of such events are intensive treatment in an emergency room or at home for allergic bronchospasm, blood dyscrasias or convulsions that do not result in hospitalization or development of dependency or abuse.

For Japan only: the following events will be handled as “deemed serious for any other reason”. AEs which possibly lead to disability will be reported as SAEs.

AEs considered “Always Serious”

Cancers of new histology and exacerbations of existing cancer must be classified as a serious event regardless of the duration between discontinuation of the drug and must be reported as described in [Section 5.2.6.2](#), subsections “AE Collection” and “AE reporting to sponsor and timelines”.

In accordance with the European Medicines Agency initiative on Important Medical Events, Boehringer Ingelheim has developed a list of further AEs, which by their nature, can always be considered to be “serious” even though they may not have met the criteria of an SAE as defined above. The latest list of “Always Serious AEs” can be found in the eDC system.

These events should always be reported as SAEs as described above.

Adverse events of special interest (AESIs)

The term AESI relates to any specific AE that has been identified at the project level as being of particular concern for prospective safety monitoring and safety assessment within this trial, e.g. the potential for AEs based on knowledge from other compounds in the same class. AESIs need to be reported to the sponsor's Pharmacovigilance Department within the same timeframe that applies to SAEs, please see above.

The following are considered as AESIs:

Hepatic injury

Hepatic Injury, is defined by the following alterations of hepatic laboratory parameters:

- An elevation of AST and/or ALT and/or AP ≥ 3 -fold ULN plus 2 times the baseline, combined with an elevation of total bilirubin ≥ 2 -fold ULN plus 1.5 times the baseline, measured in the same blood draw sample, or
- aminotransferase (ALT, and/or AST) elevations ≥ 10 fold ULN

Any patients with these lab abnormalities need to be followed up according to the 'Drug-Induced Liver Injury (DILI) checklist' provided in the ISF. In case of clinical symptoms of hepatic injury (icterus, unexplained encephalopathy, unexplained coagulopathy, right upper quadrant abdominal pain, etc.) without lab results (ALT, AST, total bilirubin) available, the investigator should make sure these parameters are analyzed, if necessary in an unscheduled blood test. Should the results meet the criteria of hepatic injury alert, the procedures described in the DILI checklist should be followed.

Systemic hypersensitivity reactions including Infusion reactions and anaphylactic reaction

Any suspicion of severe systemic hypersensitivity including infusion reactions and any anaphylactic reaction should be defined and assessed using the criteria discussed in the statement paper from Sampson HA ([Section 4.2.1.1](#) and [Appendix 10.1.6](#); ([R11-4890](#)).

Severe infections (according to RCTC grading in the ISF)

Opportunistic and mycobacterium tuberculosis infections

These include pneumocystis jirovecii, BK virus disease including PVAN, CMV, post-transplant lymphoproliferative disorder (EBV), progressive multifocal leucoencephalopathy, bartonellosis (disseminated only), blastomycosis, toxoplasmosis, coccidioidomycosis, histoplasmosis, aspergillosis (invasive only), candidiasis (invasive or pharyngeal), cryptococcosis, other invasive fungi (mucormycosis (zygomycosis, rhizopus, mucor, lichtheimia), scedosporium/pseudallescheria boydii, fusarium), legionellosis, listeria monocytogenes (invasive only), tuberculosis, nocardiosis, non-tuberculous mycobacterium, salmonellosis (invasive only), HBV reactivation, herpes simplex (invasive only), herpes zoster, strongyloides (hyperinfection syndrome and disseminated forms only),

paracoccidioides, penicillium marneffei, sporothrix schenckii, cryptosporidium species (chronic only), microsporidiosis, leishmaniasis (visceral only), trypanosoma cruzi infection (Chagas' disease) (disseminated only), campylobacteriosis (invasive only), shigellosis (invasive only), vibriosis (invasive due to vibrio vulnificus), HCV progression ([R17-2617](#)).

Protocol-specified AESI can be classified as serious or non-serious but all AESI must be reported in an expedited manner similar to serious adverse events on a SAE form (i.e. non serious AESI must be reported on the SAE form and follow the same reporting timelines as for serious AEs).

Intensity of AEs

The intensity grading of AEs will be performed according to RCTC Version 2.0 developed by the Outcome Measures in Rheumatology (OMERACT) organization ([R13-3515](#)). Refer to the ISF for intensity/severity classification.

Intensity options are:

Grade 1	mild
Grade 2	moderate
Grade 3	severe
Grade 4	life-threatening

Causal relationship of AEs

Medical judgement should be used to determine the relationship, considering all relevant factors, including pattern of reaction, temporal relationship, de-challenge or re-challenge, confounding factors such as concomitant medication, concomitant diseases and relevant history.

Arguments that may suggest that there is a reasonable possibility of a causal relationship could be:

- The event is consistent with the known pharmacology of the drug.
- The event is known to be caused by or attributed to the drug class.
- A plausible time to onset of the event relative to the time of drug exposure.
- Evidence that the event is reproducible when the drug is re-introduced
- No medically sound alternative aetiologies that could explain the event (e.g. pre-existing or concomitant diseases, or co-medications).
- The event is typically drug-related and infrequent in the general population not exposed to drugs (e.g. Stevens-Johnson syndrome).
- An indication of dose-response (i.e. greater effect size if the dose is increased, smaller effect size if dose is diminished).

Arguments that may suggest that there is no reasonable possibility of a causal relationship could be:

Proprietary confidential information © 2020 Boehringer Ingelheim International GmbH or one or more of its affiliated companies

- No plausible time to onset of the event relative to the time of drug exposure is evident (e.g. pre-treatment cases, diagnosis of cancer or chronic disease within days / weeks of drug administration; an allergic reaction weeks after discontinuation of the drug concerned)
- Continuation of the event despite the withdrawal of the medication, taking into account the pharmacological properties of the compound (e.g. after 5 half-lives). Of note, this criterion may not be applicable to events whose time course is prolonged despite removing the original trigger.
- Additional arguments amongst those stated before, like alternative explanation (e.g. situations where other drugs or underlying diseases appear to provide a more likely explanation for the observed event than the drug concerned).
- Disappearance of the event even though the trial drug treatment continues or remains unchanged.

5.2.6.2 Adverse event collection and reporting

AE Collection

The Investigator shall maintain and keep detailed records of all AEs in their patient files.

The following must be collected and documented on the appropriate CRF(s) by the investigator:

For patients rolling over into open label extension trial (1368-0025):

- From signing the informed consent of the parent trial onwards until the first dose of trial medication in the extension trial:
 - all AEs (non-serious and serious) and all AESIs.

For patients not rolling over into subsequent OLE trial (1368-0025):

- From signing the informed consent onwards until the individual patient's end of trial:
 - all AEs (serious and non-serious) and all AESIs.
- After the individual patient's end of trial:
the investigator does not need to actively monitor the patient for AEs but should only report related SAEs and related AESIs of which the investigator may become aware of by any means of communication, e.g. phone call. Those AEs should be reported on the BI SAE form, but not on the CRF.

The follow-up period describes the period of time from the last administration of trial medication until the end of trial examination (last per-protocol contact).

AE reporting to sponsor and timelines

The investigator must report SAEs, AESIs, and non-serious AEs which are relevant for the reported SAE or AESI, on the BI SAE form via fax immediately (within 24 hours) to the sponsor's unique entry point (country specific contact details will be provided in the ISF).

Proprietary confidential information © 2020 Boehringer Ingelheim International GmbH or one or more of its affiliated companies

The same timeline applies if follow-up information becomes available. In specific occasions the investigator could inform the sponsor upfront via telephone. This does not replace the requirement to complete and fax the BI SAE form.

With receipt of any further information to these events, a follow-up SAE form has to be provided. For follow-up information the same rules and timeline apply as for initial information.

Information required

For each AE, the investigator should provide the information requested on the appropriate eCRF pages and, if applicable, the BI SAE form. The investigator should determine the causal relationship to the trial medication.

The following should also be recorded as an (S)AE in the CRF and, if applicable, BI SAE form:

- Worsening of the underlying disease or of other pre-existing conditions
- Changes in vital signs, ECG, physical examination and laboratory test results, if they are judged clinically relevant by the investigator.

If such abnormalities already pre-exist prior to trial inclusion they will be considered as baseline conditions and should be collected in the eCRF only. All (S)AEs, including those persisting after a patient's end of trial, must be followed up until they have resolved, have been assessed as "chronic" or "stable", or no further information can be obtained.

Pregnancy

Urine pregnancy testing should be done prior to study drug administration. Study drug should only be administered in case of a negative test result. In case of a positive urine pregnancy test, a serum pregnancy test will be done. Women who underwent tubal ligation are still considered of childbearing potential and pregnancy testing is necessary as well. The testing schedule is specified in the [Flow Chart](#).

In rare cases, pregnancy might occur in a clinical trial. Once a patient has been enrolled in the clinical trial and has taken trial medication, the investigator must immediately (within 24 hours) report any drug exposure during pregnancy by means of Part A of the Pregnancy Monitoring Form to the sponsor's unique entry point.

[figure not shown]
The outcome of the pregnancy associated with the drug exposure during pregnancy must be followed up and reported to the sponsor's unique entry point on the Pregnancy Monitoring Form for Clinical Trials (Part B).

The ISF will contain the Pregnancy Monitoring Form for Clinical Trials (Part A and B).

As pregnancy itself is not to be reported as an AE, in the absence of an accompanying SAE and/or AESI, only the Pregnancy Monitoring Form for Clinical Trials and not the SAE form

Proprietary confidential information © 2020 Boehringer Ingelheim International GmbH or one or more of its affiliated companies

is to be completed. If there is an SAE and/or AESI associated with the pregnancy an SAE form must be completed in addition.

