2.1.4 Secondary endpoints

Secondary Endpoints at Week 4:

Secondary Endpoints of the study at Week 4 which are included in the statistical testing strategy in a hierarchical manner subsequent to performance of the tests on the primary endpoint and key secondary endpoint (see [Section 7.2](#)) are:

- A Psoriasis Area and Severity Index for Generalized Pustular Psoriasis (GPPASI) 75 at Week 4.
- Change from baseline in Pain Visual Analog Scale (VAS) score at Week 4.
- Change from baseline in Psoriasis Symptom Scale (PSS) score at Week 4.

Proprietary confidential information © 2020 Boehringer Ingelheim International GmbH or one or more of its affiliated companies

- Change from baseline in Functional Assessment of Chronic Illness Therapy (FACIT) Fatigue score at Week 4.

Other secondary endpoints of the study at Week 4 are:

- A Generalized Pustular Psoriasis Physician Global Assessment (GPPGA) score of 0 or 1 at Week 4.
- A GPPGA pustulation sub-score of 0 indicating no visible pustules at Week 4.
- A GPPASI 50 at Week 4.
- The percent reduction in GPPASI from baseline at Week 4.

For the estimand concept on each of the above-defined binary secondary endpoint definition(s) at week 4, any use of escape medication prior to Week 4, or OL BI 655130 use at D8, or any rescue medication with BI 655130 prior to Week 4 will be considered to represent a non-response at the Week 4 timepoint. For continuous endpoints, refer to [Section 7.3.3](#).

Secondary Endpoints at Week 1:

[figure not shown]
Additional secondary endpoints of the study at week 1, where (for binary endpoint(s) only), any use of escape medication prior to week 1 will be considered to represent a non-response at the Week 1 timepoint, are:

- A GPPASI 50 at Week 1.
- The percent reduction in GPPASI from baseline at Week 1.

Secondary Safety Endpoints:

The following safety endpoint is also defined:

- The occurrence of Treatment Emergent Adverse Events (TEAEs)

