3. DESCRIPTION OF DESIGN AND TRIAL POPULATION

3.1 OVERALL TRIAL DESIGN AND PLAN

This is a multicenter, randomized, double-blind, placebo-controlled Phase II study with one dose of BI 655130/placebo in patients with GPP presenting with an acute flare of moderate to severe intensity. The primary objectives of this trial are to assess the efficacy, safety and tolerability of a single intravenous (i.v.) dose of BI 655130 in comparison to placebo in patients with generalized pustular psoriasis (GPP) presenting with an acute flare of moderate to severe intensity.

Approximately 11 to 20 countries will participate by using sites/centers experienced in the management of GPP.

Fifty-one patients with generalized pustular psoriasis (GPP) presenting with an acute flare of moderate to severe intensity are required to be randomized to receive BI 655130/ placebo (2:1) into this trial.

Patients are considered enrolled (screened) in the study once they have signed the informed consent.

Patients eligible to receive treatment after screening will be able to participate in this study and will be randomized at a ratio of 2:1(BI 655130/Placebo) to one of two treatment groups as shown in [Figure 3.1: 1](#). All patients will receive the first dose of study medication (900 mg i.v. BI 655130 or Placebo) on Day 1 of Week 1 (Randomization). Based on the subsequent treatment response patients will then be followed for 12 to 28 weeks (see [Flow Chart](#)). Study Week in the flow chart represents the end of each week (e.g. End of Wk1=D8, End of Wk2 =D15, End of Wk3 = D22, End of Wk4 =D29 etc.).

During Week 1, D1, D2, D3 and D8 are mandatory visits, however, D4 – D7 are optional visits and need not be attended if a patient has already achieved complete pustular clearance (GPPGA pustulation sub score =0) at the previous visit.

At the discretion of the investigator, patients may be hospitalized prior to, during or following first study drug administration. Thereafter, the decision to discharge a patient from the hospital will also be at the discretion of the investigator, based on the evolution of the GPP flare and the patient's health status.

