7.3.5 Safety analyses

Adverse events will be coded using the current version of Medical Dictionary for Regulatory Activities (MedDRA) coding dictionary. Standard BI summary tables and listings will be produced.

All treated patients will be included in the safety analysis. In general, safety analyses will be descriptive in nature and will be based on BI standards. No hypothesis testing is planned. Statistical analysis and reporting of adverse events will concentrate on treatment-emergent adverse events. To this end, all adverse events occurring between start of treatment and end of the residual effect period will be considered 'treatment-emergent'; the residual effect period (REP) is defined as 16 weeks after the last dose of trial medication. Note that for patients who continue into the extension trial, TEAE up to the first dose in the extension trial will be available for display in the current study. Adverse events that start before first drug intake and deteriorate under treatment will also be considered as 'treatment-emergent'. For all subjects who received OL BI 655130 at D8 or rescue medication with BI 655130, safety assessments including adverse events, laboratories, vital signs etc. which occurred subsequent to such intake will be excluded from presentations according to the planned treatments; these data will, however, be included in summaries where all data after any use of BI 655130 are displayed.

Frequency, severity, and causal relationship of adverse events will be tabulated by system organ class (SOC) and preferred term after coding according to the current version of the MedDRA.

The exposure adjusted incidence rate (per 100 subject years) of a selected treatment emergent adverse event is defined as the number of subjects experiencing the adverse event per treatment group during time at risk divided by the total time of subjects at risk in that treatment group to contribute the event to the analysis multiplied by 100 (per 100 subject years), where:

[figure not shown]
$$\text{Time at risk [subject years]} = (\text{date of onset of TEAE} - \text{study drug start date} + 1) / 365.25$$

[figure not shown]

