End of time at risk post use of rescue medication with Spesolimab will be the min of (the day of rescue medication with Spesolimab in the trial +112 or the last contact date per EoS page if patient will not be rolled over or the day prior to first dose in the extension study if patient will be rolled over).

In addition, for overall period post use of any Spesolimab,

Time at risk overall post use of any Spesolimab [subject years] = (date of onset of TEAE up to the end time of risk – first use of any Spesolimab start date + 1) / 365.25

End of time at risk for overall post use of any Spesolimab will be min of (the day of last Spesolimab in the trial +112 or the last contact date per EoS page if patient will not be rolled over or the day prior to first dose in the extension study if patient will be rolled over).

The analyses of AEs will be descriptive in nature. All analyses of AEs will be based on the exposure adjusted incidence rates (per 100 subject years), as well as the number of patients with AEs and not on the number of AEs. System organ classes (if applicable) will be sorted according to the standard sort order specified by the EMA, preferred terms (if applicable) will be sorted by total frequency (within system organ class) across all treatment columns, cf. [Section 6.1](#).

For further details on summarization of AE data, please refer to "Handling and summarization of adverse event data for clinical trial reports and integrated summaries" ([7](#)) and "Handling of missing and incomplete AE dates" ([4](#)).

The analysis of AEs will be based on the concept of treatment emergent AEs. This means that all AEs will be assigned to the screening phase, treatment phase or follow-up phase as

defined in [Section 6.1](#). Since only the start date of an AE is collected (without start time), any AE occurrence on the same day as randomized Spesolimab/placebo administration will be assigned to the on-treatment period.

An overall summary of AEs will be presented. This overall summary will include summary for the class of AESIs.

The following are considered as AESIs ([see Sec 5.2.6.1 of CTP](#)):

- Hepatic injury
- Systemic hypersensitivity reactions including Infusion reactions and anaphylactic reaction
- Severe infections (according to RCTC grading in the ISF)
- Opportunistic and mycobacterium tuberculosis infections

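### The pooled TEAE and SAE rows include GPP worsening, with no planned summary that leaves it out; this probably tilts the Week 1 comparison towards spesolimab

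*Protocol*

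**What the plan says.** - **Recording.** Protocol 5.2.6.2: "The following should also be recorded as an (S)AE in the CRF and, if applicable, BI SAE form", followed by "Worsening of the underlying disease or of other pre-existing conditions". GPP is not exempted.
- **Treatment-emergence.** Protocol 7.3.5: "all adverse events occurring between start of treatment and end of the residual effect period will be considered" treatment-emergent, the residual effect period (REP) being 16 weeks. Also, "Adverse events that start before first drug intake and deteriorate under treatment will also be considered as" treatment-emergent.
- **Seriousness.** Protocol 5.2.6.1 makes an AE serious if it "requires inpatient hospitalization" or prolongs an existing stay. No flare exception is written. Protocol 3.1 leaves admission to the investigator: "patients may be hospitalized prior to, during or following first study drug administration".
- **Endpoint and tables.** The occurrence of TEAEs is the secondary safety endpoint (Protocol 2.1.4). SAP 7.8.1: "The analysis of AEs will be based on the concept of treatment emergent AEs". It plans an overall summary; tables by system organ class (SOC) and preferred term; separate tables for SAEs, drug-related events, AESIs and user-defined AE concepts (UDAECs); and a table by maximum intensity. None leaves out the disease under study, and no UDAEC covers it.
- **Windows and censoring.** SAP 7.8: the primary safety analysis runs to Day 85, and AE tables are repeated to Week 1 and to the end of the REP. Data after open-label Day 8 or rescue spesolimab are censored, and an AE on the day of such a dose moves to the later period. SAP 6.6.3 keeps data after escape medication.

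**The concern.** Worsening of GPP acts on both sides of the benefit-risk balance. It is the usual reason for escape medication, which before Week 1 makes the patient a non-responder (Protocol 2.1.2, Table 3.1:1). It is also an AE, and a serious one if it leads to admission. An effective drug therefore lowers the any-TEAE and any-SAE rows through its efficacy, whatever its tolerability.

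The primary objective includes safety and tolerability compared with placebo (Protocol 2.1.1), and the trial is to support first registration (Protocol 1.3). With 17 placebo patients, a few worsening events can create an apparent safety advantage in the pooled rows, or offset a true excess of other events on the drug.

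**Working it through.** **1. Planning figures.** The documents state no expected TEAE, SAE or worsening rate, so there is none to reproduce. What they do state is the expected efficacy contrast: Week 1 response of 0.6 v 0.1 (Protocol 7.7). SAP 7.5.2 also expects most placebo patients to have taken escape medication by Day 8 or open-label spesolimab at Day 8. The power quoted for 0.6 v 0.1 (96.3% for the primary endpoint, 93.9% for both endpoints) recomputes to 96.3% and 93.8% and does not depend on this point.

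**2. Who stays in the randomized comparison.** A patient given escape medication in Week 1 cannot have the Day 8 open-label dose (Protocol 3.1). SAP 6.6.3 keeps that patient's later data in the randomized arm unless rescue spesolimab follows. So the patients who worsen most are retained. For the Week 1 table, risk ends at the drug stop date plus 6 days (SAP 7.8.1), that is Day 7, before any Day 8 dose. Both arms then have about 7 days.

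**3. Size in a pooled row.** Let b be the non-disease TEAE rate and w the worsening-AE rate. If the two are independent within patients:

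any-TEAE = 1 − (1 − b)(1 − w)

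If b is equal in both arms, gap = (1 − b)(w placebo − w active).

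All rates below are assumptions, with b = 50%:

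| w, placebo v active | any-TEAE, placebo v active | gap |
|---|---|---|
| 20% v 5% | 60.0% v 52.5% | 7.5 points |
| 30% v 5% | 65.0% v 52.5% | 12.5 points |
| 40% v 10% | 70.0% v 55.0% | 15.0 points |

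Tolerability is identical in every row. With b = 30%, the first and last gaps become 0.7 × 15 = 10.5 and 0.7 × 30 = 21 points. Independence matters too. If only patients who already have another TEAE worsen, the gap is 0. If none of them do, it is the full difference in w (15 to 30 points).

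**4. Masking.** Suppose a true excess on the drug: b = 30% placebo, 50% active (+20 points).
- w = 20% v 5%: 44.0% v 52.5%, so +8.5 points.
- w = 50% v 10%: 65.0% v 55.0%, so −10 points.

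With worsening terms excluded, the difference is +20 in both cases.

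**5. Weight of one patient.** On placebo 1/17 = 5.9 points; on spesolimab 1/34 = 2.9 points. Placebo exposure to Week 1 is at most 17 × 7/365.25 = 0.326 subject-years, so one event adds about 100/0.326 = 307 per 100 subject-years, ignoring the small loss of time at risk.

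**6. Longer windows.** Censoring works the other way. Assume a constant hazard giving 50% over 84 days. A patient censored after 7 days then has an event probability of 1 − 0.5^(7/84) = 5.6%. If 80% of placebo patients are censored then, the crude placebo rate is 0.8 × 5.6% + 0.2 × 50% = 14.5% instead of 50%. That could outweigh the worsening events.

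**7. Recovering the total from planned tables.** SAP 7.8.1 counts patients, not events. A patient with GPP worsening and headache appears once under any TEAE, so subtracting the GPP row does not give the total without it. The same holds for any SAE, the SOC total and maximum intensity.

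**The case against.** Much of the case on the other side stands.

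- **A reader might infer that the TEAE endpoint counts efficacy failure.** It does not. Only worsening is recorded. Missing a pustulation subscore of 0 or a GPPGA of 0 or 1 is not an AE, and Table 3.1:1 separates worsening from a stable condition. Escape use is not the same event either: SAP 7.2 includes escape for disease that has not improved.
- **A reader might infer that drug-related harm is hidden.** The tables do not support that for specific harms. Other preferred-term rows, AESIs, UDAECs, laboratory results and local tolerability are untouched. Drug-related tables are probably little affected, since Protocol 5.2.6.1 names underlying disease as an argument against causality.
- **Every flare admission would not be an SAE.** An SAE must first be an AE. Discretionary admission for the qualifying flare, without worsening, does not meet the definition by itself.
- **Listings allow a rebuild.** SAP 7 lists all individual values, and 51 patients can be counted by hand. But the terms would then be chosen after the arms are known, which is what a SAP should prevent.
- **Safety is descriptive.** No hypothesis is tested, so no error rate is at stake. The pooled rows will still be read as a between-arm comparison.
- **Some text is not visible.** The section on AE subgroups and the sponsor's AE guideline could not be read. The finding of absence rests on SAP 7.8 and 7.8.1 as shown.
- **Excluding terms has a risk.** Worsening caused by the drug, or rebound, would leave the table. This argues against replacing the all-TEAE comparison or removing these terms from the drug-related table.

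**Conclusion.** The point holds for the pooled rows: any TEAE, any SAE, the SOC total to which GPP terms code (presumably skin) and maximum intensity. If the drug works, these rows are likely to be tilted towards spesolimab, most clearly in the Week 1 table. For the crude Week 12 and REP percentages the net direction is not established, because shorter placebo follow-up pulls the other way.

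The illustrative size is 7.5 to 15 points. It rests on an assumed 50% non-disease TEAE rate in both arms, assumed worsening rates of 20% v 5% to 40% v 10%, independence and equal follow-up. The recording rule applies to both arms, so the imbalance is an expectation drawn from the planned efficacy contrast, not a documented rate. The collection rule is not at fault, and the efficacy analyses and power are unaffected. This is a cheap improvement to the safety reporting.

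**What to change.** Keep AE collection unchanged and keep the all-TEAE tables as the main display. In SAP 7.8.1 add:

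1. A preferred-term list for GPP or pustular-psoriasis worsening, fixed before unblinding; if the primary and final analyses are run separately, that means before the primary-analysis unblinding.
2. Supplementary any-TEAE, any-SAE and severe-AE summaries that exclude those terms, by frequency and exposure-adjusted rate, for Week 1 first and then Week 12 and the REP. For the exposure-adjusted rate, run time at risk to the first counted event.
3. The excluded events by arm, beside both sets of tables, so that drug-induced or rebound worsening stays visible.

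Do not make the reduced summaries the main tolerability comparison, and leave the drug-related tables as they are. The cost is a short term list and one repeat of existing table shells, with no new data.
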